## 8.2. Setting

Events of pregnancy are reported to Pfizer:

- via clinical trials (when clinical trial participant reports pregnancy during trial);
- via non-interventional studies (eg, THAOS B3461001);
- via spontaneous reporting (post-marketing);
- through direct contact from patients and health care professionals;
- through unsolicited requests for pregnancy safety information (via Pfizer Medical Information Department);
- through contact with sales representatives.

Both maternal and paternal exposure to tafamidis were historically captured in TESPO, however, since initiation of this program it has been determined in nonclinical studies that the risk for male-mediated developmental toxicity is considered low. Consequently, exposure during pregnancy due to paternal exposure will not be required to be captured in Study B3461091.

For EDP cases occurring during sponsored clinical trials investigators are trained on how to report the case to the Sponsor, using standard PV forms.

For all other reportings, information regarding how to contact the Sponsor (per country specific labeling guidelines) in the event of a known pregnancy exposure is provided in the SmPC, the USPI, the PIL, and in informational materials provided (eg, scientific meetings and direct communication) to HCPs.

## 8.2.1. Inclusion Criteria

Patients must meet all of the following inclusion criteria to be eligible for inclusion in the study:

All women diagnosed with ATTR exposed to tafamidis during or within 1 month prior to pregnancy, reported as exposure during pregnancy (EDP) events in interventional or non-interventional clinical studies in the tafamidis development program, via spontaneous reports, solicited cases or compassionate use reports, will be included in study B3461091.

## 8.2.2. Exclusion Criteria

There are no exclusion criteria for this study.

## 8.3. Variables

Variables to be evaluated in this study include patient medical/obstetrical history and pregnancy status and outcomes, neonate and infant development status at birth, and at 6 and 12 months of age.

Variable	Description	Data Source
Maternal status		
Obstetrical History Number of pregnancies Outcome of previous pregnancies	Number of pregnancies including current pregnancy Outcomes of previous pregnancies (full term/premature live birth, stillbirth, etc) Number of living children, children born with congenital anomalies History of infertility	EDP form
Date of first day of last menstrual period	DD-MMM-YYYY	EDP form
Estimated date of conception	DD-MMM-YYYY	EDP form
Tafamidis Exposure	Formulation and dosage. Start and stop dates of tafamidis	EDP form
Exposure to concomitant medications that have risk of congenital abnormalities	Dose and start and stop dates of these concomitant medications	EDP form
Gestational age at exposure	Gestational age of fetus at exposure to tafamidis or other medication (weeks or trimester)	EDP form

PFIZER CONFIDENTIAL

CT24-WI-GL02-RF02 1.0 Non-Interventional Study Protocol Template For Secondary Data Collection Study 15-Aug-2018 Page 19 of 42

Variable	Description	Data Source
Medical History Risk Factors	Risk factors for adverse pregnancy outcomes (ie, environmental exposures, eg, hypertension, diabetes, etc.	EDP form
	Family history of congenital abnormality/genetic diseases	
Smoking	Type and number per day	EDP form
Alcohol use	Type and frequency	EDP form
Illicit drug use	Type and frequency	EDP form
Current Pregnancy		,
Maternal assessment at time of study enrollment	Vital Signs BP, temp, pulse	
Smoking during pregnancy	Type and number per day	EDP form
Alcohol use during pregnancy	Type and frequency	EDP form
Illicit drug use during pregnancy	Type and frequency	EDP form
Other relevant medical conditions, use of concomitant medications, other exposures to drugs	Comorbities/hospitalizations during pregnancy/other concomitant medications or treatments taken during pregnancy	EDP form
Maternal assessment during 2 nd trimester	Vital Signs BP, temp, pulse	EDP form

Variable	Variable Description			
Smoking during pregnancy	Type and number per day	EDP form		
Alcohol use during pregnancy	Type and frequency	EDP form		
Other relevant medical conditions, use of concomitant medications, other exposures to drugs	Comorbities/hospitalizations during pregnancy/other concomitant medications or treatments taken during pregnancy	EDP form		
Maternal assessment at delivery				
Smoking during pregnancy	Type and number per day	EDP form		
Alcohol use during pregnancy Type and frequency		EDP form		
Other relevant medical conditions, use of concomitant medications, other exposures to drugs	onditions, use of oncomitantduring pregnancy/other concomitant medications or treatments taken during			
Child status				
Neonate health status at birth	Gender, head circumference, length (cm or in), birth weight (kg or lbs)	EDP form		
	Survival, any congenital anomalies diagnosed,			

Variable	Description	Data Source
	(chromosomal testing results if performed), any medical conditions diagnosed/treated	
Neonate developmental status	Age-appropriate developmental milestones achieved or delayed	EDP form
Infant exposure during breast-feeding	Length of exposure, any interruptions in exposure	Tafamidis enhanced surveillance follow up form
Infant health status at 6 months	Survival, any congenital anomalies diagnosed, (chromosomal testing results if performed), any medical conditions diagnosed/treated	Revised form
	Weight (kg or lbs), length (cm or in), Hospitalizations during the	
	first 6 months	
Infant developmental status at 6 months	Age-appropriate developmental milestones achieved or delayed	Revised form
Child status at 12 months		
Health status at 12 months	Survival, any congenital anomalies diagnosed, (chromosomal testing results if performed), any	Tafamidis enhanced surveillance

Variable	Description	Data Source
	medical conditions diagnosed/treated Weight (kg or lbs), length (cm or in), Hospitalizations during the first year	follow up form
Developmental status of infant at 12 months	Age-appropriate developmental milestones achieved or delayed	Tafamidis enhanced surveillance follow up form
Medication/vaccination status at 12 months	Medications taken during the first year, vaccinations received	Tafamidis enhanced surveillance follow up form

## 8.4. Data Sources

The data source for this study is what is maintained in the Pfizer safety database, ARGUS (standard pharmacovigilance forms for clinical studies and the data collection forms used in the TESPO surveillance program), and described in Section 8.2.

## 8.5. Study Size

Sample size calculations are not applicable. All pregnant women diagnosed with ATTR meeting the inclusion criteria presented in Section 8.2.1 will be included in this study.

## 8.6. Data Management

# 8.6.1. Case Report Forms (CRFs)/Data Collection Tools (DCTs)/Electronic Data Record Process for Enhanced Surveillance

As used in this protocol, the term CRF[/DCT] should be understood to refer to either a paper form or an electronic data record or both, depending on the data collection method used in this study. For this study the data collection forms are considered the CRF.

Reported neonate and infant adverse events associated to EDPs in women exposed to tafamidis will be entered by the Pfizer Data Safety Unit (DSU) as a separate adverse event from the EDP case (cases will be linked) in the safety database. These infant adverse event cases will then be followed-up via the standard process (Table 2) used for all safety reports in order to obtain all available information. This process applies to both clinical and spontaneous EDP reports.

Case Type	1 st Follow-Up Attempt	2 nd Follow-Up Attempt	Minimum Requirements
Clinical Studies	Within 10 calendar days for SRD 	20 calendar days after 1 st f/u  attempt	
 
For Pfizer-sponsored clinical studies: 2 f/u attempts and:
 
If contact with site is established, continue until all f/u information is obtained.
 
If no response from site after 2 attempts, escalate with standard "Follow-up Escalation Notice" to obtain information.
 
For non-Pfizer-sponsored clinical studies: 2 f/u attempts and case closed as per standard Pfizer DSU procedure.
 

Non-Clinical Sources:	Within 10 calendar days for SRD	20 calendar days after 1 st f/u attempt	Two follow-up attempts and case closed as per standard Pfizer DSU procedure.

Table 2.	Timelines for Follow-Up Requests and Additional Follow-up Attempts
----------	--

: SRD: Safety Receipt Date; : f/u: follow-up; : DSU: Drug Safety Unit. Source: Pfizer internal Standard Operating Procedures.

For clinical EDP cases with associated neonate and infant adverse events, the investigator is responsible for securing patient consent and collecting detailed information. For post-marketing cases the patient reporting the infant adverse event, and the patient HCP if consented by the patient, will be responsible for providing detailed information. Data on infant adverse events may be collected via three avenues: the EDP Follow-Up Form, the TESPO Form and the separate infant case process.

The revised TESPO Form Question 7 captures if major congenital anomaly(ies) has/have been confirmed by a physician. The standard EDP Follow-Up form documents congenital malformation/anomalies at birth and "diagnosed" anomalies for the neonate or infant (implies physician diagnosis).

All reports of exposure during pregnancy will be captured per regulatory and Sponsor policy in the pharmacovigilance database.

PFIZER CONFIDENTIAL

In addition to routine pharmacovigilance surveillance for women with ATTR exposed to tafamidis, additional data on pregnancy and outcome and infant status at birth, 6 and 12 month post-delivery will be collected via the data collection forms used in TESPO. In TESPO, all reported cases of tafamidis EDP and pregnancy outcomes including spontaneous abortion, birth defects and other adverse pregnancy outcomes or developmental deficits in infants will be captured in the Pfizer safety database and coded according to the current version of Medical dictionary for regulatory activities (MedDRA).

A data capture aid and/or standard Serious Adverse Event (SAE) and follow-up form will be completed for each included patient. The completed forms are the sole property of Pfizer and should not be made available in any form to third parties, except for authorized representatives of Pfizer or appropriate regulatory authorities, without written permission from Pfizer. The reporter shall ensure that the forms are securely stored at the site (or equivalent) in a secured location to prevent access by unauthorized third parties.

## Pfizer Clinical Study Serious Adverse Event Report

If a woman with ATTR taking tafamidis in a Pfizer-sponsored clinical study becomes pregnant, a clinical trial (CT) SAE Report Form will be completed by the Investigator, as stated in the study protocol. When the SAE report is received by the local Pfizer DSU, the local Pfizer DSU staff enters the information contained in the CT SAE Report Form into Pfizer's global safety database (ARGUS) and follows up with the investigator per standard follow–up practices for missing/discrepant/clarifying information on the CT SAE Report Form. The investigator addresses DSU queries for clarifying the initial SAE report and will use the CT Follow-up Form.

## Serious Adverse Event Exposure During Pregnancy Supplemental Report (EDP) Form

This form is to be completed for all reported exposures during pregnancy, regardless of source of report. Upon receipt of information concerning an exposure to tafamidis of a woman during or within 1 month prior to pregnancy, or a reported pregnancy occurring within one month of tafamidis discontinuation, the reporter will complete a standard EDP form. This form is to be submitted to the local Pfizer DSU. If the initial contact is not an obstetric HCP, women will be requested to sign and send a release form to the reporter, which authorizes the Sponsor to contact the obstetric HCP for additional information. When the EDP report is received by the local Pfizer DSU, the local Pfizer DSU staff enters the information contained in the EDP Form into Pfizer's global safety database (ARGUS) and follows up with the investigator per standard follow–up practices for missing/discrepant/clarifying information. The investigator addresses DSU queries for clarifying the initial EDP report and will complete the query form or an additional EDP form.

The initial completed form will collect basic demographic information, medical and obstetrical history (for patient and family), pregnancy information including estimated due date and dates of all drug exposures within 1 month of pregnancy.

At the midpoint of the pregnancy and the estimated time of delivery, the obstetric HCP will be asked to complete an additional standard EDP form with reference to the status and outcome of the pregnancy. The local Pfizer DSU staff enters the information contained in the EDP Form into Pfizer's global safety database (ie, Argus) and follows up with the HCP per standard follow–up practices for missing/discrepant/clarifying information. The HCP addresses DSU queries for clarifying the follow up EDP report and will complete the query form or an additional EDP form. This form will be submitted to the local Pfizer DSU by fax (or email, if approved by Pfizer).

## Tafamidis Enhanced Surveillance for Pregnancy Outcomes (TESPO) 6 and 12-Month Infant Follow-up

In the event of a live birth, the obstetric HCP will be sent a release form to be signed by the female individual to allow the Sponsor to contact the infant's pediatric HCP for additional infant outcome data. The Sponsor will contact the pediatric HCP to complete the TESPO Infant 6 and 12-Month Follow-up Form by phone or fax.

If anomalies are noted on the EDP Form or the TESPO Infant Follow-up Forms, a more detailed investigation may be initiated by the Sponsor.

Measures of pregnancy and birth outcomes	Common abbreviation	Definition
Preterm birth	РТВ	Birth at less than 37 completed weeks of gestation
Very preterm birth	VPTB	Birth at less than 32 completed weeks of gestation
Low birth weight	LBW	Weighing less than 2,500 grams (~5.5 pounds) at delivery
Very low birth weight	VLBW	Weighing less than 1,500 grams (~3.3 pounds) at delivery
Infant mortality	IM	Death of a live-born infant before the first birthday
Fetal death (stillbirth)	FD	Death of a fetus after the 20 th week of gestation
Spontaneous fetal losses	SFL	Recognized pregnancies that do not result in induced abortions or live births; includes miscarriages, ectopic (tubal) pregnancies, and FD

Centers for Disease Control (CDC) - Measures of birth and pregnancy outcomes

Definition of SFL from Ventura SJ, et al. 2004.

According to the CDC congenital anomalies comprise a wide range of abnormalities of body structure or function that are present at birth and are of prenatal origin. For efficiency and practicality, the focus is commonly on *major* structural anomalies. These are defined as structural changes that have significant medical, social or cosmetic consequences for the affected individual, and typically require medical intervention. Examples include cleft lip and spina bifida. Major structural anomalies are the conditions that account for most of the deaths, morbidity and disability related to congenital anomalies. In contrast, minor congenital anomalies, although more prevalent among the population, are structural changes

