1. Describe birth outcome frequency within the reported pregnancies (live full term or premature birth, spontaneous or induced abortion, and stillbirth) in women with ATTR exposed to tafamidis during or within 1 month prior to pregnancy.

2. Describe the frequency of reported fetal, neonate and infant outcomes within the reported pregnancies (major congenital malformations/anomalies [overall and specific], low birth weight, small for gestational age (SGA), preterm birth, low Apgar score at 1 and 5 minutes, and infant milestone status at 6 and 12 months) following tafamidis exposure in women with ATTR during or within 1 month prior to pregnancy.

**Population:** Women diagnosed with ATTR who received tafamidis during pregnancy or who became pregnant within 1 month after discontinuation of tafamidis reported as EDP events in interventional or non-interventional clinical studies in the tafamidis development program, via spontaneous reports, solicited cases or compassionate use reports, and who agreed to release information from their obstetric and pediatric healthcare provider will be included in this study.

**Study Design**: This is a global, prospective, non-interventional study designed to collect and report information obtained via TESPO and/or standard EDP and follow-up information on outcomes of events of pregnancy in women with ATTR exposed to tafamidis during pregnancy or who became pregnant within 1 month after discontinuation of drug.

**Variables:** Variables to be evaluated in this study include patient medical /obstetrical history, pregnancy status and outcomes, and neonate and infant development status at birth, 6 and 12 months of age.

**Data Sources:** Events of pregnancy reported in female patients with ATTR receiving tafamidis via clinical trials, non-interventional trials, through direct contact from patients and health care professionals using the toll-free numbers provided in the labeling documents, through unsolicited requests for pregnancy safety information (via Pfizer Medical Information Department) or through contact with sales representatives. Information regarding how to contact the Sponsor (per country specific labeling guidelines) in the event of a pregnancy exposure is provided in the summary of product characteristics (SmPC), the US package insert (USPI), the patient information leaflet (PIL), and in informational materials provided (e.g., scientific meetings and direct communication) to health care professionals (HCPs).

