## 9.2. Patient Consent

The information used in this study is anonymized (ie, the information per se does not identify any patient and cannot be used to re-identify the patients with the available information) before the study is conducted. Therefore, no study-specific consent form is required for this study. However, women participating in TESPO or in sponsored clinical trials will be asked to provide agreement for a release of information from their obstetric and pediatric healthcare provider(s).

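### The only described request for the pediatric release comes after a live birth and through the obstetric provider, so 12-month infant follow-up can depend on the infant's known condition, even in prospective cases

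*Protocol*

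**What the plan says.** Section 8.6.1 describes two releases, sought at different times.

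- **Obstetric release (EDP Form heading).** If the initial contact is not an obstetric provider, "women will be requested to sign and send a release form to the reporter". This release serves for approaching the obstetric provider only. Where an obstetric provider makes the report, no release is described at this stage.
- **Pediatric release (TESPO 6 and 12-Month Infant Follow-up heading).** "In the event of a live birth, the obstetric HCP will be sent a release form to be signed by the female individual". Its purpose is permission to approach the child's own provider, who is the source of the later infant data. The next step is stated as follows: "The Sponsor will contact the pediatric HCP to complete the TESPO Infant 6 and 12-Month Follow-up Form by phone or fax".

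The condition at birth is reported at about the same time: "At the midpoint of the pregnancy and the estimated time of delivery, the obstetric HCP will be asked to complete an additional standard EDP form".

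Two other places mention a pediatric release, and neither gives a time. Section 9.2 says that women in TESPO or sponsored trials will be asked to agree to release of information from both kinds of provider. The Abstract's population paragraph refers to women "who agreed to release information from their obstetric and pediatric healthcare provider will be included in this study".

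Infant milestone status at 6 and 12 months is an Objective 2 outcome (Section 7).

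**The concern.** Section 8.7 separates prospective from retrospective cases by whether the woman enrolled before the pregnancy outcome, because reporting that follows the outcome can be selective. The infant follow-up does not keep to that principle. A woman may enrol early in pregnancy, yet the one described request for permission to contact the child's provider reaches her after delivery, when she and the obstetric provider know how the infant is. It also goes through a provider whose last scheduled form is at delivery.

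Two things follow. Some infants may be lost who could have been kept, and the loss may be related to the infant's health. The second matters more, because the percentages for milestone delay and late-diagnosed anomalies would then describe a selected set of infants. Section 6.2.2 reports postnatal mortality and impaired learning and memory in rat offspring, which are effects of the kind that later follow-up would have to detect.

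**Working it through.** **Step 1: is an earlier pediatric request described?**

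| Place in the protocol | Provider covered | When requested |
|---|---|---|
| 8.6.1, EDP Form | Obstetric only | First report, if the first contact is not an obstetric provider |
| 8.6.1, TESPO infant follow-up | Pediatric | After a live birth, through the obstetric provider |
| 9.2 | Both | No time given |
| Abstract, Population | Both | No time given |

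The only pediatric request with a stated time comes after birth.

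**Step 2: which data depend on it?**

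- *Status at birth* (Section 8.3) comes from the EDP form and does not need this release.
- *12 months*: Section 8.3 names the enhanced surveillance follow-up form, which 8.6.1 has the pediatric provider complete. These data rest on the release.
- *6 months*: Section 8.1 names the standard EDP Follow-Up Form, Section 8.3 a revised form, and 8.6.1 the TESPO infant form. Dependence on the release is unsettled.
- *Infant adverse events*: Section 8.6.1 gives three avenues, including a separate linked case. The linked case serves only infants with a reported event.

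**Step 3: how large could the effect be?** The protocol states no follow-up rate, so there is no figure to reproduce. Let p be the true proportion affected, and fa and fu the shares followed among affected and unaffected infants. All three are assumptions.

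observed proportion = p × fa / (p × fa + (1 − p) × fu)

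For p = 0.10, fa = 0.90, fu = 0.60: 0.09 / (0.09 + 0.54) = 0.09 / 0.63 = 14.3%. With the rates swapped: 0.06 / (0.06 + 0.81) = 0.06 / 0.87 = 6.9%.

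| True p | fa = fu = 70% | 90% / 60% | 60% / 90% | 90% / 30% | 30% / 90% |
|---|---|---|---|---|---|
| 5% | 5.0% | 7.3% | 3.4% | 13.6% | 1.7% |
| 10% | 10.0% | 14.3% | 6.9% | 25.0% | 3.6% |
| 20% | 20.0% | 27.3% | 14.3% | 42.9% | 7.7% |

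(Columns give fa / fu.) Equal follow-up gives no bias; unequal follow-up gives bias in either direction.

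**Step 4: in counts.** Section 6 reports 13 maternal exposures up to 25 September 2019. Purely to show scale, assume 13 live births, 1 affected and 4 not followed. The true proportion is 1/13 = 7.7%. The observed proportion is 1/9 = 11.1% if the affected infant is followed and 0/9 = 0% if that infant is lost.

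**The case against.** **An earlier request is not excluded.** A reader might infer that the protocol forbids or rules out asking before birth. It does not: Section 9.2 and the Abstract leave the time open. What stands is that no procedure provides for an earlier request.

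**Infants with problems have other routes.** The linked adverse event case, with investigators securing consent in clinical studies and patients supplying details after marketing, may favour affected infants. This counts against inferring that delay would be understated. It does not remove the concern, since a route open only to infants with a reported event is itself dependent on condition.

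**Waiting until birth is defensible.** A pediatric provider may not exist earlier, and some jurisdictions may require a signature after birth. Retrospective cases cannot be asked earlier at all. This limits what a change can achieve.

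**The loss is already disclosed, and numbers are small.** Section 8.9 admits that infant follow-up may be missing and promises every effort to obtain it, but does not say that missingness may depend on the infant's condition. On size, moving from 10% to 6.9% or 14.3% is a shift of 3.1 or 4.3 percentage points, less than the 7.7 points that one infant in 13 represents. In a descriptive study without hypothesis testing this keeps the point modest. Even so, Step 4 shows that following or losing one affected infant can decide whether any delay is reported.

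**Selective follow-up would be partly visible.** Status at birth is collected, so comparing infants with and without follow-up on that status would give some evidence of selection. It would be wrong to call the bias undetectable.

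**Conclusion.** The point holds as a weakness in the design of the infant follow-up that is cheap to improve. On the only procedure described, permission for the 12-month pediatric follow-up is sought after the infant's condition is known, in prospective cases as well. The same applies at 6 months if the TESPO infant form is used instead of the EDP Follow-Up Form. The Objective 2 percentages for milestones and late-diagnosed anomalies can be biased in either direction. The size is unknown, and the figures above illustrate assumed rates only.

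Two stronger readings are not supported. One is that the birth outcomes are compromised: they come from the EDP form and do not need this release. The other is that inclusion in the study depends on a decision after birth. The Abstract's wording invites that reading, but Sections 8.2.1 and 8.2.2 include every reported woman and state no exclusions. Those passages should be reconciled, but the present point stands even if every reported woman is included.

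**What to change.** In Section 8.6.1:

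1. For women reported before the pregnancy outcome, request the pediatric release at enrolment, whoever the reporter is, together with the obstetric release where one is needed.
2. After delivery, ask only for the pediatric provider's name, with re-confirmation where local law requires it.
3. Let the mother return the form directly as well as through the obstetric provider.
4. Report the number of live-born infants with a release, and with completed 6- and 12-month follow-up, split by status at birth (anomaly, preterm or low birth weight versus none) and by prospective versus retrospective case.
5. State one source form for the 6-month data, so that Sections 8.1, 8.3 and 8.6.1 agree.

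The cost is one extra form at enrolment and some protocol wording. Some signatures after birth will still be needed, and some women will not yet have a pediatric provider. Because the mother must still name the provider after delivery, the dependence is reduced and made visible, but not eliminated. Retrospective cases gain only the direct return route and the tabulation.
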